**Table 5: Scoring of Non-Lesional Erythema** 

Severity	Score	Description
None	0	No erythema
Mild	1	Light pinkness present
Moderate 2		Definite redness, easily recognized
Severe	3	Intense redness

**Table 6: Scoring of Peeling** 

Severity	Score	Description
None	0	No peeling
Mild	1	Barely perceptible shedding, noticeable only on light scratching or rubbing
Moderate	2	Obvious but not profuse shedding
Severe	3	Heavy scale production

**Table 7: Scoring of Dryness** 

Severity	Score	Description
None	0	No dryness
Mild	1	Slight barely perceptible fine superficial scale
Moderate	2	Clearly perceptible fine scale giving skin a powdery appearance
Severe	3	Marked roughness, cracked skin with fissures

**Table 8: Scoring of Stinging** 

Severity	Score	Description
None	0	No stinging
Mild	1	Slight sharp, tingling/stinging sensation; not really bothersome
Moderate	2	Definite sharp, tingling/stinging sensation; that is somewhat bothersome
Severe	3	Sharp, tingling/stinging sensation that has caused definite discomfort

**Table 9: Scoring of Burning** 

Severity	Score	Description
None	0	No burning
Mild	1	Slight warm, burning sensation; not really bothersome
Moderate	2	Definite warm, burning sensation; that is somewhat bothersome
Severe	3	Hot, burning sensation that has caused definite discomfort

**Table 10: Scoring of Itching** 

Severity	Score	Description
None	0	No itching
Mild	1	Slight itching; not really bothersome
Moderate	2	Definite itching that is somewhat bothersome, without loss of sleep
Severe	3	Intense itching that has caused pronounced discomfort; night rest interrupted and excoriation of the skin from scratching may be present

**Table 11: Overall Tolerance** 

Grades	Score	Description
Excellent	0	No signs of irritation during the study
Good	1	Slight signs of irritation during the study, which
		resolved by the end of the study
Fair	2	Signs of irritation throughout the study
Poor	3	Subject discontinued due to irritation
Irritation is defined as any sign or symptom of intolerance.		

# 7.7 Early Withdrawal of Subjects

- 1. Subjects should be withdrawn from the study if they no longer wish to participate, are being uncooperative, or if the investigator feels that it is in the best interest of the subject to withdraw.
- 2. Subjects with protocol deviations or for whom it is discovered should have been excluded should not be withdrawn unless there is a safety concern. The protocol deviation should be recorded in the subject's chart and Protocol Deviation Form and included in the study report.
- 3. Subjects who experience an AE resulting in or requiring discontinuation of study product use should be encouraged to be followed in the study until the AE is resolved or stabilized.
- 4. Subjects whose treatment randomization is unblinded at the study site should be withdrawn.

- 5. If a female subject becomes pregnant during the study, study product will be discontinued immediately and she will be followed through the pregnancy and delivery. Details of the pregnancy, delivery and health of the infant should be recorded on the Pregnancy Report Form and the sponsor notified immediately.
- 6. At the time of study discontinuation, the investigator will record the reason for early withdrawal, date of last study product application, date of last visit or contact, collect AE data, and, if possible, perform all Week 12 visit-specific evaluations. Every attempt should be made to contact subjects who are lost-to-follow-up for a final safety assessment. At least three attempts must be documented in the subject's chart including the use of at least 1 certified letter. Any contact, either direct or indirect, should be made with the purpose to document the final status of the subject with regard to safety.
- 7. Subjects who withdraw early will not be replaced.

### 7.8 Modification of Protocol

No amendments to this protocol can be made without consultation with and agreement of the sponsor, the FDA, and IRB. Amendments must be made in writing. Modifications needed for the safety of subjects will be made immediately with notifications made as soon as possible.

### 7.9 Early Termination of Study

If it is determined by the sponsor or investigators that the study presents an unreasonable and significant risk to subjects, the study will be terminated as soon as possible, and in no event later than 5 working days following the determination that the study should be discontinued. The IRB and FDA must be notified as soon as possible about early termination of the study due to safety concerns.

### 7.10 Study Schedule

A Study Schedule chart can be found as Table 1. There are approximately 5 study visits: Screening (Visit 1), Baseline (Visit 2, Day 1), Week 4 (Visit 3), Week 8 (Visit 4), and Week 12 (Visit 5). The visit window is  $\pm$  3 days for Week 4 and  $\pm$  5 days for Weeks 8 and 12. Visit 1 and Visit 2 should not be separated by more than 60 days.

The Screening Visit (Visit 1) and the Baseline Visit (Visit 2) may be combined into a single visit if no washout is required. In that case, complete the required procedures for each visit as listed below.

## 7.10.1 Visit 1 - Screening Visit

- 1. Obtain written assent and/or informed consent prior to initiating any study procedures. Provide subject with signed copy of Information and assent/consent form. Document assent and/or informed consent in the subject's study record.
- 2. List subject on Screening Log and assign a screening number. Screening numbers consist of the 3-digit site number followed by sequential 3-digit numbers usually starting with 001 (e.g., 806001, 806002, 806003). All subjects will be assigned a screening number.

- 3. Perform a urine pregnancy test on all female subjects.
- 4. Collect demographic data date of birth, sex, race, and ethnicity.
- 5. Review and record medical history, acne history (including naïve vs previous therapy, acne treatment received 12 months prior to screening, onset date for acne and first acne treatment, previous use of Tazorac and any issue with Tazorac use), and concomitant medications, therapies, and procedures. Medical history and acne history should be collected for the prior 1-year period and concomitant medications, therapies, and procedures collected from the prior 6-month period. Only ongoing medical history items and ongoing concomitant medications should be entered on the eCRF. Acne history will be collected and recorded in the eCRF.
- 6. Assess severity of acne using IGA (record on source only). IGA assessments should always be done prior to lesion counts.
- 7. Conduct inflammatory and non-inflammatory lesion counts of the face (record on source only).
- 8. Collect vital signs (blood pressure and pulse) (record on source only).
- 9. Screen subject according to the study inclusion/exclusion criteria to determine tentative eligibility.
- 10. Initiate any protocol-required washout, if applicable.
- 11. Schedule Visit 2.
- 12. Complete eCRF for randomized subjects. For every screen failure subject, record the subject number, date of visit, date of consent, reason for screen failure, and study status (screen failure) in the eCRF.

### 7.10.2 Visit 2 - Day 1, Baseline Visit

If no washout is required, Screening and Baseline may occur on the same day.

- 1. Update the medical history and concomitant medications. Any medical event (not related to a protocol intervention) that occurred since 'Information and assent/informed consent form was signed should be recorded as medical history. Only ongoing medical conditions and ongoing concomitant medications should be entered on the eCRF.
- 2. Collect AEs. Any new medical event or need for medication caused by a protocol procedure performed at the Screening Visit should be considered an AE except for worsening of acne.
- 3. Confirm eligibility according to inclusion/exclusion criteria.
- 4. Conduct urine pregnancy test on all female subjects. Record method of contraception, as applicable, on source only.
- 5. Perform a physical examination.
- 6. Collect vital signs (blood pressure and pulse), height and weight, and record Fitzpatrick skin type.

### 7. Conduct clinical assessments:

- a. IGA for the face (Table 4). IGA assessments should always be done prior to lesion counts.
- b. Count inflammatory and non-inflammatory lesions on the face and, if applicable, on chest and/or back (including shoulders) for selected site(s). These counts should be recorded separately for the face and, if applicable, chest and/or back (including shoulders) for selected site(s).
- c. Local cutaneous safety evaluation for dryness, non-lesional erythema, and peeling. The investigator should also ask the subject if any burning, stinging, or itching has occurred on the face in the last 14 days. These evaluations should be recorded separately for the face and, if applicable, chest and/or back (including shoulders) for selected site(s).
- 8. Administer the CADI questionnaire.
- 9. The independent third party study medication dispenser will perform the following procedures:
  - a) Assign a subject number using the subject kit #. Randomize subject by using the lowest available number of study kit at the study site.
  - b) Weigh and then dispense 2 bottles or 1 tube of study product (depending on the treatment assignment) to subjects. For the selected site(s) who will enroll subjects with acne on the chest and/or back, weigh and dispense 4 bottles or 2 tubes of study product. The tear-off panel is to be affixed to the source document and filed in subject's chart. Instruct subject on study product use. Review the Subject Instructions with subject. Instruct subject to not discuss study product with Investigator or other study staff.
  - c) Supervise the first application of study product at the site to ensure that it is done correctly.
  - d) Remind subject to bring all bottles or tubes of study product to next visit.
  - e) Dispense and review use of diary. Remind subject to report missed applications and/or potential AEs as well as any medication used in the diary and to bring diary to each visit.
- 10. Schedule next visit.
- 11. Complete eCRF for randomized subjects. For every screen failure subject, record the subject number, date of visit, date of consent, reason for screen failure, and study status (screen failure) in the eCRF.

## 7.10.3 Visit 3 – Week 4/Day 28 (Visit Window $\pm$ 3 Days)

- 1. Evaluate treatment and protocol compliance and record any deviations. This includes a review of the diary card for number of applications and missed applications.
- 2. Conduct clinical assessments:
  - a. IGA for the face (Table 4). IGA assessments should always be done prior to lesion counts.
  - b. Count inflammatory and non-inflammatory lesions on face and, if applicable, on chest

- and/or back (including shoulders) for selected site(s). These counts should be recorded separately for the face and, if applicable, chest and/or back (including shoulders) for selected site(s).
- c. Local cutaneous safety evaluation for dryness, non-lesional erythema, and peeling. The investigator should also ask the subject if any burning, stinging, or itching has occurred on the face since the last visit. These evaluations should be recorded separately for the face and, if applicable, chest and/or back (including shoulders) for selected site(s).
- 3. Administer the CADI questionnaire.
- 4. Collect vital signs (blood pressure and pulse).
- 5. Conduct a urine pregnancy test for all females.
- 6. Collect AE data. This includes a review of the diary card for potential AEs.
- 7. Update concomitant medications data.
- 8. The independent third party study medication dispenser will perform the following procedures:
  - a) Dispense diary and review instructions. Remind subject to bring all bottles or tubes of study product to each visit.
  - b) Weigh and then dispense study product, 1 new bottle or 1 new tube, and collect used bottles or tubes. For the selected site(s) who will enroll subjects with acne on the chest and/or back, weigh and dispense, or 3 bottles or 2 tubes of study product. Weigh bottles or tubes when they are collected. Redispense old bottles/tubes as needed. Instruct subject to not discuss study product with Investigator or other study staff.
- 9. Schedule next visit.
- 10. Complete eCRF.

## 7.10.4 Visit 4 - Week 8/Day 56 (Visit Window $\pm$ 5 Days)

- 1. Evaluate treatment and protocol compliance and record any deviations. This includes a review of the diary card for number of applications and missed applications.
- 2. Conduct clinical assessments:
  - a. IGA for the face (Table 4). IGA assessments should always be done prior to lesion counts
  - b. Count inflammatory and non-inflammatory lesions on face, and, if applicable, on chest and/or back (including shoulders) for selected site(s). These counts should be recorded separately for the face and, if applicable, chest and/or back (including shoulders) for selected site(s).
  - c. Local cutaneous safety evaluation for dryness, non-lesional erythema, and peeling. The investigator should also ask the subject if any burning, stinging, or itching has occurred on the face since the last visit. These evaluations should be recorded separately for the face and, if applicable, chest and/or back (including shoulders) for selected site(s).

- 3. Administer the CADI questionnaire.
- 4. Collect vital signs (blood pressure and pulse).
- 5. Conduct a urine pregnancy test for all female subjects.
- 6. Collect AE data. This includes a review of the diary card for potential AEs.
- 7. Update concomitant medications data.
- 8. The independent third party study medication dispenser will perform the following procedures:
  - a) Dispense diary and review instructions. Remind subject to bring all bottles or tubes of study product to each visit.
  - b) Weigh and then dispense study product, 1 new bottle or 1 new tube, and collect used bottles or tubes. For the selected site(s) who enroll subjects with acne on the chest and/or back, weigh and dispense 3 bottles or 2 tubes of study product to subjects. Weigh bottles or tubes when they are collected. Redispense old bottles/tubes as needed. Instruct subject to not discuss study product with Investigator or other study staff.
- 9. Schedule next visit.
- 10. Complete eCRF.

## 7.10.5 Visit 5 – Week 12/Day 84/End of Treatment (Visit Window $\pm$ 5 Days)

- 1. Evaluate treatment and protocol compliance and record any deviations. This includes a review of the diary card for number of applications and missed applications.
- 2. Conduct clinical assessments:
  - a. IGA for face (Table 4). IGA assessments should always be done prior to lesion counts.
  - b. Count inflammatory and non-inflammatory lesions on face and, if applicable, on chest and/or back (including shoulders) for selected site(s). These counts should be recorded separately for the face and, if applicable, chest and/or back (including shoulders) for selected site(s).
  - c. Local cutaneous safety evaluation for dryness, non-lesional erythema, and peeling. The investigator should also ask the subject if any burning, stinging, or itching has occurred on the face since the last visit. In addition, overall cutaneous tolerance should be graded at the Week 12 visit, or the last visit if earlier, using the grading shown in Table 11. These evaluations should be recorded separately for the face and, if applicable, chest and/or back (including shoulders) for selected site(s).
- 3. Administer the CADI questionnaire.
- 4. Perform physical examination.
- 5. Collect vital signs (blood pressure, pulse).
- 6. Collect AE data. This includes a review of the diary card for potential AEs.
- 7. Update concomitant medications data.

- 8. Conduct a urine pregnancy test for all female subjects.
- 9. The independent third party study medication dispenser will perform the following procedures:
  - a) Collect study diary.
  - b) Collect and weigh all study product bottles or tubes.
- 10. Complete eCRF.

## 7.10.6 Unscheduled Visit (If Applicable)

### Conduct the following, as needed.

- 1. Evaluate treatment and protocol compliance and record any deviations.
- 2. Collect vital signs (blood pressure and pulse).
- 3. Collect AE data. This includes a review of the diary card for potential AEs.
- 4. Update concomitant medications data.
- 5. The independent third party study medication dispenser will weigh and then dispense/re-dispense, collect and weigh study product, as needed.
- 6. Conduct a urine pregnancy test for all females.
- 7. Complete eCRF.

### 8 ADVERSE EVENTS

Adverse events will be collected by spontaneous reports from subjects, either verbal or recorded in the subject diary, by directed questioning of subjects, and by observation.

The most common frequently reported adverse reactions during clinical trials with tazarotene cream 0.1% for the treatment of acne were desquamation, dry skin, erythema, and burning sensation, occurring in 10% to 30% of subjects. Adverse reactions occurring in 1% to 5% of treated subjects included pruritus, irritation, face pain, and stinging.

The investigator is to pay special attention at each visit to any signs of clinically significant dryness, non-lesional erythema, and peeling and report as an AE subsequent to the Baseline Visit if worse than at Baseline.

An AE is any untoward medical occurrence in a subject participating in a clinical trial. The event does not necessarily have to have a causal relationship with the study product. An AE can therefore be any sign, symptom, or disease, or any worsening of an existing sign, symptom, or disease, whether or not considered related to the study product or trial procedures, including injuries.

Any medical condition that is present at the time of Screening or Baseline should be considered as medical history and reported on the medical history eCRF and should not be reported as an AE except for AEs observed at the Baseline Visit due to study procedures performed at the Screening visit, which should be reported. Anticipated day-to-day fluctuations of pre-existing conditions should not be reported as AEs. Unexpected worsening of pre-existing conditions should be reported as AEs. The disease or condition being studied or expected progression,

signs, or symptoms of the disease or condition being studied such as worsening of acne should not be reported as an AE unless it is more severe than expected, results in discontinuation from the study or requires alternative therapy.

All serious adverse events (SAEs), all study product-related events, and all AEs leading to study product discontinuation must be followed until the clinical outcome is determined or until all attempts to determine resolution of the event are exhausted (not recovered is not an acceptable outcome for acute conditions). For other AEs, the status at the last visit can be entered into the eCRF.

## 8.1 Adverse Event Reporting Period

Adverse event data must be collected from the time treatment is initiated until study product treatment is discontinued except for spontaneously reported SAEs, which should be reported up to 30 days after discontinuing study product use and entered into the eCRF. Adverse events occurring from the time of the Screening Visit until the Baseline Visit associated with study procedures should also be reported for all subjects, including screen failures.

## **8.2** Recording Adverse Events

The investigator will record all AEs, regardless of relationship to study product on the AE eCRF. Standard medical terminology should be used when describing AEs. Whenever possible a diagnosis should be made and recorded on the eCRF rather than listing signs and symptoms. Intermittent AEs can be recorded once. The anatomical location of the AE must be specified when applicable. The following information should be recorded on the eCRF:

- 1. Description, including whether on treated area or not
- 2. Start date
- 3. Stop date or date of death, ongoing, or unknown
- 4. Severity of the event (see Section 8.3.1 Severity for details)
- 5. Study product use continued or not
- 6. Outcome of the event (recovered/resolved, recovered/resolved with sequelae, not recovered/not resolved, unknown, fatal)
- 7. Relationship to study product (see Section 8.3.2 Relationship to Study Product [Causality] for details)
- 8. Indication of whether the event is serious (see Section 8.3.3 Seriousness for details)
- 9. Actions taken including treatment with concomitant medication

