### 7.6 Safety Assessments

Safety assessments include vital signs, local cutaneous tolerance evaluation of the treated skin, and AEs. Vital signs (blood pressure and pulse) will be collected at each visit. A physical examination will be performed at Baseline (Day 1) and at Week 12. Urine pregnancy tests for all female subjects (regardless of childbearing potential) will be conducted at Screening and Baseline (Day 1) and at each subsequent visit. Adverse events will be collected by spontaneous reports from subjects (either verbal or recorded in the subject diary), by directed questioning of subjects, and by observation (see Section 8 for details about AEs). Adverse events, whether believed by the investigator to be related or unrelated to treatment, will be recorded on the eCRF.

At Visits 2 through 5 the investigator will assess local cutaneous tolerance by examining treated areas for clinically significant non-lesional erythema, peeling, and dryness that will be graded as shown below (Table 5, Table 6, Table 7) and recorded on the eCRF. Assessments will be recorded separately for the face and (if applicable) chest and/or back (including shoulders) for selected site(s). The investigator will also ask the subject if any stinging (Table 8), burning (Table 9), or itching (Table 10) has occurred on the face and chest and/or back (including shoulders), if applicable since the last visit (for Visit 2 in the last 2 weeks). Visit 2 assessments are made prior to first application. An AE should be recorded if the severity is worse than at Baseline. In addition, overall cutaneous tolerance should be graded at the Week 12 visit, or the last visit if earlier, using the grading shown in Table 11. The local cutaneous tolerance signs and

symptoms will be assessed separately for the face and chest and/or back (including shoulders), if applicable, for selected site(s), using the same scales below.

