3.2. Study Endpoints

3.2.1. Primary Endpoints

The primary safety endpoints are:

- Local Cutaneous Safety Evaluation Data (dryness, non-lesional erythema, peeling, stinging, burning, and itching). Reactions on the face were assessed separately from those on the chest/back/shoulders.
- Treatment-Emergent Adverse Events (TEAEs).

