9.3.4. Summaries of Adverse Events

Adverse event verbatim text will be coded and classified by system organ class (SOC) and preferred term (PT) using the MedDRA (Version 20.0). AE summary tables will use the following algorithms for counting subject events within the summary tables:

- Any event row: Each subject with an event is counted only once at the maximum grade although they may have several events. For drug related AE tables, each subject with an event is counted only once at the most related although they may have several events.
- System organ class rows: Each subject is counted only once at the maximum grade at each system organ class level although they may have several different preferred term events within the same SOC.
- Preferred term rows: Each subject is counted once within each unique preferred term at the maximum grade. Subjects experiencing the same AE preferred term several times with different grades would only be counted once with the maximum grade.

For partially missing start or stop dates, the imputation rule specified in Section 6.8.3 will be applied before assessing if an AE was a TEAE.

TEAE data will be summarized by treatment and overall.

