9.3.4.1. Overview and Summaries of Adverse TEAEs

An overall summary table (overview) of all TEAEs will be presented, summarizing:

- Total Number of TEAEs
- Total Number of TESAEs
- Total Number of TEAESIs
- Number of Subjects with at Least One TEAE
- Number of Subjects with at Least One Related TEAE
- Number of Subjects with at Least One Severe (Grade 3) TEAE
- Number Subjects with at Least One TEAE Leading to Treatment Discontinuation
- Number Subjects with at Least One TEAE Leading to Death
- Number of Subjects with at Least One TESAE
- Number of Subjects with at Least One Related TESAE
- Number of Subjects with at Least One TEAESI

[name], Ltd Statistical Analysis Plan, Version 2.0

TEAEs will be summarized by SOC and PT. For SOC, each subject is counted only once at each SOC level although they may have several different PT events within the same SOC. Likewise for any PT event, each subject with an event is counted only once although they may have several PT events that are the same.

Summaries for the common TEAEs will be created for TEAEs with an incidence [> 1%] in at least one treatment group. Common TEAEs will be summarized by SOC and PT.

Summaries for TEAEs by maximum severity will be created for all TEAEs. Severity will be summarized by SOC and PT. If a subject has multiple occurrences of the same SOC or PT, then only the most severe event will be summarized in the tables for that SOC or PT. TEAEs with missing severity treatment will be counted as severe.

Summaries for TEAEs by the closest relationship to study drug will be created for all TEAEs. Relationship to study drug will be summarized by SOC and PT. TEAEs will be classified as "Related" to study drug if relationship is categorized as Definitely Related, Probably Related or Possibly Related. Otherwise TEAEs will be classified as "Not Related". If a subject has multiple occurrences of the same SOC or PT, then only the most related event will be summarized in the tables for that SOC or PT. TEAEs with missing relationship to study drug will be counted as "Related".

TEAE outcomes will be summarized by SOC and PT. TEAE outcome categories are:

- Recovered/Resolved
- Recovered/Resolved with Sequelae
- Not Recovered/Not Resolved
- Fatal
- Unknown

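### Protocol 8.2 is not reconciled with 7.6 and Section 8 on whether a worsened local reaction is recorded as its signs or as one diagnosis, so preferred-term rates and TEAE totals depend on site practice

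*Protocol*

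**What the plan says.** **Recording rules.** Protocol 8.2, in the general instructions for the AE page: "Whenever possible a diagnosis should be made and recorded on the eCRF rather than listing signs and symptoms". It makes no exception for local skin reactions. It also asks for the anatomical location and whether the event lies on the treated area.

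Protocol 7.6 has the investigator grade erythema, peeling and dryness and ask about stinging, burning and itching. It then adds: "An AE should be recorded if the severity is worse than at Baseline". Section 8 directs attention at each visit to "any signs of clinically significant dryness, non-lesional erythema, and peeling", with the instruction to "report as an AE subsequent to the Baseline Visit if worse than at Baseline".

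**Analysis.** SAP 3.2.1 lists two primary safety endpoints: the local cutaneous evaluation and TEAEs. For the second, SAP 9.3.4.1 says "TEAEs will be summarized by SOC and PT", and SAP 9.3.4 gives the counting rule: "Each subject is counted once within each unique preferred term at the maximum grade". The overview table also reports the total number of TEAEs, subjects with at least one TEAE, subjects with at least one related TEAE, and TEAEs of special interest (TEAESI). SAP 9.3.1 defines AE, TEAE and SAE, but TEAESI is defined nowhere.

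**Background rates.** For tazarotene cream 0.1% in acne, Section 8 cites "desquamation, dry skin, erythema, and burning sensation, occurring in 10% to 30% of subjects". It lists irritation as a separate reaction at 1% to 5%.

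**The concern.** A site that sees erythema, dryness and peeling worsen in one subject can enter three terms, following 7.6 and Section 8, or one diagnosis, following 8.2, and defend either choice. The protocol itself supplies an umbrella word: the footnote to its Overall Tolerance table defines irritation to cover any sign or symptom of intolerance, while Section 8 counts irritation apart from the individual signs. Both ways of recording are therefore realistic.

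The trial is descriptive, so the tabulated rates are themselves the comparison of lotion with cream. If the choice of term varies between sites, the preferred-term rates of a primary endpoint mix two conventions. If it varies between arms, part of any difference in a preferred-term row could be labelling. The SAP has no row specific to local reactions that would bring the two conventions back together.

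**Working it through.** The plan states no power, effect size or event count for this endpoint, so there is no figure to reproduce. The check is a comparison of the texts followed by an illustration.

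**1. The instructions side by side**

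| | Protocol 7.6 | Protocol Section 8 | Protocol 8.2 |
|---|---|---|---|
| Question answered | When is an AE recorded? | When is an AE recorded? | What term does it carry? |
| Scope | Sentence follows all six graded items | Three signs, if clinically significant | All AEs, no exception |
| Strength | Should be recorded | Instruction to report | Whenever possible |
| One AE or several for concurrent signs? | Not stated | Not stated | Favours one diagnosis |
| Which rule prevails? | Not stated | Not stated | Not stated |

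The rules can be read together, but not in only one way.

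**2. Inputs.** Arm sizes (Protocol 6.4): 150 × 2/6 = 50 per active arm and 150 × 1/6 = 25 per vehicle arm. Sign rates p of 10% to 30% (Section 8). One count per subject per preferred term (SAP 9.3.4). The share f of affected subjects whose signs are entered as one diagnosis is not in the documents, so the full range 0 to 1 is shown.

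**3. Worked case.** Ten of 50 subjects each have worsened erythema, dryness and peeling.

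| Recorded as | Sign terms | Diagnosis term | Total TEAEs | Subjects with any TEAE |
|---|---|---|---|---|
| Signs | three at 10/50 = 20% | 0% | 10 × 3 = 30 | 10/50 = 20% |
| Diagnosis | three at 0% | 10/50 = 20% | 10 | 10/50 = 20% |

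**4. General form.** Reported sign rate = p × (1 − f).

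| p | f = 0 | 0.25 | 0.5 | 0.75 | 1 |
|---|---|---|---|---|---|
| 10% | 10% | 7.5% | 5% | 2.5% | 0% |
| 20% | 20% | 15% | 10% | 5% | 0% |
| 30% | 30% | 22.5% | 15% | 7.5% | 0% |

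**5. Between arms.** With the same true p in both arms, the artificial gap is p × (difference in f). At p = 30%:

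- equal shares: 0 points;
- 25% versus 50%: 22.5% − 15% = 7.5 points;
- 25% versus 75%: 22.5% − 7.5% = 15 points.

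These shares are assumptions. The protocol's own irritation figure suggests smaller ones. If subjects with irritation and subjects with a given sign did not overlap (also an assumption), the umbrella share would run from 1/(30 + 1) = 3% to 5/(10 + 5) = 33%, and would be at most 5/(30 + 5) = 14% beside a 30% sign rate. Shares of 0% versus 14% at p = 30% give 30% versus about 26%, a gap of about 4 points. Those rates come from earlier trials whose recording rule the documents do not give, so they do not settle the share here.

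**6. Scale.** The 95% half-width for a 50 versus 50 difference is 1.96 × √(2p(1 − p)/50): 11.8, 15.7 and 18.0 points at p = 10%, 20% and 30%. Even the 15-point illustration lies inside the sampling uncertainty at 30%.

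**The case against.** A reader might infer that the sections contradict each other and that every worsened sign must be its own AE. The text does not go that far. 7.6 and Section 8 set a trigger, 8.2 governs terminology and only where a diagnosis is possible, and Section 8 names three signs with a clinical-significance qualifier. Letting the specific rule override the general one is a natural reading. The documents simply do not say so.

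A reader might also infer that staff who know lotion from cream would label the arms differently. Protocol 6.5.1 does leave site staff unblinded to product group, but it also keeps the assessing investigator and the staff who assess AEs away from dispensing and returns, and tells subjects not to discuss the medication with them. The shield is partial: AE collection at Weeks 4, 8 and 12 includes review of a diary that records application times, and twice-daily versus once-daily use reveals the product. This makes differential labelling possible. It does not show that it happens.

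The strongest objection is that much of the tolerability comparison does not pass through AE terms. All six reactions are scored 0 to 3 and tabulated by arm and visit (SAP 9.2), with a repeat that excludes subjects who had signs at Baseline. Overall Tolerance is summarized by treatment. Each arm also has rows for subjects with any TEAE and any related TEAE. All of this stands. It limits the point to preferred-term rates and event totals, and it gives a cross-check on any odd result there.

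**Conclusion.** The point holds as an unreconciled ambiguity. Preferred-term rates and the total TEAE count of a primary endpoint depend on a recording choice that the plan leaves to the site. In the worked case the same ten subjects yield 30 events or 10, and three sign rates of 20% or 0%. The any-TEAE and related-TEAE subject rows, the graded scores and Overall Tolerance are essentially unaffected, and no planned test or power figure is involved.

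A bias between arms would require labelling that differs by arm. If all sites followed one rule, the terms would shift in every arm. The 15-point gap is an illustration that rests on assumed shares of 25% and 75%. The documents support neither that figure nor any other, and equal shares give no gap. The change is worth making because it is cheap, not because a large distortion has been shown.

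**What to change.** **Protocol 8.2 and the eCRF completion guide.** State that each of the six graded local reactions (non-lesional erythema, peeling, dryness, stinging, burning, itching) that meets the 7.6 trigger is recorded under its own term with location, and that a diagnosis does not replace these terms.

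**SAP 9.3.4.1 and Table 14.3.1.1.** Add one row per arm: subjects with at least one local-reaction TEAE, pooling the sign terms and any irritation or dermatitis diagnosis and counting each subject once. Defining the currently undefined TEAESI category in this way would also fill that gap. The list of pooled terms should be fixed before unblinding.

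The protocol sentence helps only data still to be recorded. The pooled row works under either practice, and SAP Section 2 lets the plan change until it is finalized before database lock.

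**Cost.** One sentence, one row and a term list. There will be more AE records, so event totals rise. Where a diagnosis is entered as well, a subject counts under more than one preferred term, so the preferred-term rows should not be added together.
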